Study Title: A Single arm, Multicenter, Prospective, Clinical Study on a Novel Minimally Invasive Posterior Sacroiliac Fusion Device: **SECURE STUDY**

Principal Investigator:

[name]

Medical Monitors

[name]
[name]

Version date: April 4, 2022

Sponsor: PainTEQ

Version date: 04 April 2022

Principal Investigator: [name]

Medical Monitors: [name] and [name].

Study Title: A Single arm, Multicenter, Prospective, Clinical Study on a Novel Minimally Invasive Posterior Sacroiliac Fusion Device: **SECURE STUDY**

Co- Investigator(s): up to 10 sites

Table of Contents

I. Purpose, Background and Rationale	3
II. Research Plan and Design	3
III. Subject Participation	8
IV. Data Collection and Protection	9
V. Data Analysis and Reporting	9
VI	13
Bibliography / References	13

I. Purpose, Background and Rationale

The purpose of this post-market study is to evaluate data and evidence on the safety and efficacy of utilizing the LinQ system for sacroiliac disease. SI fusion has been a long-standing treatment for refractory SI joint disease that has failed conservative treatment. SI joint disease accounts for approximately 30-40% of all low back pain according to a recently published literature. Recently newer techniques have been developed to treat SI joint dysfunction in a less invasive method. A lateral approach utilizing three triangular titanium implants resulted in a statistically significant improvement in pain and disability when compared to conservative management for SI joint dysfunction. Although this approach is less invasive than a true open approach, it still carries significant risk and invasiveness. Risk of laterally placed screws into the spinal canal poses risk of neurological compromise. Non-weight bearing status, incisional pain, and recovery time are significant factors that must be acceptable to the clinician and patient.

Recently, an FDA approved posteriorly placed allograft into the mid-portion of the SI joint has shown significant promise as an alternative option to traditional or lateral SI fusion. The LinQ system is a minimally invasive, percutaneous, single incision technique for SI fusion. Utilizing a posterior approach eliminates the risk of spinal canal compromises and improves the overall safety profile. Additionally, using a single incision and avoiding screws reduces invasiveness and significantly reduces recovery times. A recent abstract presented by Pyles on 20 consecutive patients showed an average 83% reduction in pain at 3 months with no serious adverse effects or complications using the LinQ system[3]. The purpose of this multicenter, prospective, clinical series is to further establish the data, efficacy, and safety on the LinQ system for chronic Sacroiliac Joint Disease.

II. Research Plan and Design

A. Study Objectives:

The purpose of this post-market study is to gather evidence documenting the performance and clinical outcomes associated with treatment of sacroiliac disease with the LinQ fusion procedure.

B. Study Type and Design

Multicenter Center, Prospective, Single arm Clinical study

C. Sample size, statistical methods, and power calculation:

Anticipated study enrollment will be ongoing patients for registry.

Power calculation based on paired T test, Alpha 0.05, Beta 0.2, Power 0.8, Effect Size 0.5, two sided yielded sample size of 34 patients. Assuming a 20 percent loss to follow up or study exit rate, fifty patients would be sufficient to achieve study aims.

Statistical methods would include paired T tests for quantitative measures which include VAS score, Oswestry Disability Index, and Promis-29.

D. Subject Criteria:

Inclusion criteria:

- Age 21-70
- Patient has lower back pain for >6 months inadequately responsive to conservative care
- Patient has at least 3 of 4 physical examination maneuvers specific for the SI joint (FABER, Gaenslen test, Stork/Gillete, and Yoman)
- Patient has improvement in lower back pain numeric rating scale (NRS) of at least 50% after injection of local anesthetic into affected SI joint(s) with confirmed arthrogram, within 30-60 min from injection
- Degenerative sacroiliitis as SIJ mediated in the context of either radiographic evidence of SIJ degeneration, evident on computed tomography or Xrays or a history of prior lumbar fusion.
- SIJ disruption was defined in the study as SIJ mediated pain in the context of asymmetric widening of SIJ on CT or Xrays or the presence of significant contrast leakage during diagnostic SIJ block
- Baseline Oswestry Disability Index (ODI) score of at least 30%
- Baseline Low back/buttock pain score of at least 50 on 0-100 mm visual analog scale
- Patient has signed study-specific informed consent form
- Patient has the necessary mental capacity to consent and participate and is physically able to comply with study protocol requirements
- Patient has medical insurance that covers this standard of care procedure and all other anticipated and unanticipated procedure related care.
- Patient's physician has decided that the best treatment for the patient's sacro-iliac disease is the LinQ system and the patient has agreed to the treatment.

Exclusion criteria:

- Inability to confirm that the pain is arising from the sacroiliac joint
- Current severe back pain due to other causes, such as lumbar disc degeneration, lumbar disc herniation, lumbar spondylolisthesis, lumbar spinal stenosis, lumbar facet degeneration, lumbar radicular pain, and lumbar vertebral body fracture
- SIJ pain secondary to inflammatory conditions, Other known sacroiliac pathology such as: Sacral dysplasia, Inflammatory sacroiliitis (e.g., ankylosing spondylitis or other HLA-associated spondylo-arthropathy), Tumor, Infection, Acute fracture, and Crystal arthropathy.
- Radicular pain extending beyond the buttock \geq 30mm on VAS
- Has complete resolution of pain from the diagnostic SIJ injection lasting 30 days or more
- Has had an injection with corticosteroid into the index SIJ within the last 30 days
- Has had any neuraxial injection with corticosteroid within the last 30 days

- Has greater than 50% pain relief from diagnostic medial branch blocks at the L4/5 and/or L5/S1 levels
- Has had a sacral radiofrequency ablation within the last 6 months
- History of any hardware placement within the sacrum or sacroiliac joint. Fusion at L5/S1 is allowed if screws/hardware are not within THE Sacroiliac joint. Any hardware or instrumentation that would obstruct the ability to access or place the Linq implant would be exclusionary.
- History of coccydynia or coccygectomy
- Clinical diagnosis of discogenic pain at L4/5 and/or L5/S1
- History of endometriosis or pudendal neuralgia
- History of recent (<1 year) major trauma to pelvis
- Chronic rheumatologic condition (e.g., rheumatoid arthritis)
- Any condition or anatomy that makes treatment with the Linq Implant System infeasible
- Use of medications known to have detrimental effects on bone quality and soft-tissue healing (metabolic bone disease, induced or idiopathic)
- Prominent neurologic condition that would interfere with physical therapy
- Current local or systemic infection that raises the risk of surgery
- Patient currently receiving or seeking worker's compensation, disability remuneration, and/or involved in injury litigation.
- Patient is participating in an investigational study or has been involved in an investigational study within 3 months prior to evaluation for participation
- Patient with insurance coverage that does not cover the SI fusion*
- Implanted intrathecal pain pump

Withdrawal/Termination criteria:

- Patient's participation will only be withdrawn by their request. There are no criteria for termination of participation due to safety.

E. Specific methods and techniques used throughout the study

Study Design: The PainTEQ study is a prospective, multi-site, prospective, single arm study intended to collect clinical data outcomes data associated with the treatment of sacroiliac disease with the LinQ fusion procedure. Data will be collected using self-report measures including the visual analog scale (VAS) for pain assessment where the participant is asked to place a line perpendicular to the VAS line at the point that represents their pain intensity. Using a ruler, the score is determined by measuring the distance (mm) on the 10-cm line between the "no pain" anchor and the patient's mark, providing a range of scores from 0-100. Other self-report questionnaires will be administered including the Oswestry Disability Index (ODI) to measure low-back pain and disability, and the PROMIS 29 to measure physical, mental, and social health and well-being. The study team will also collect data including:

- Patient Satisfaction with Procedure
- Opioid consumption (Morphine Milligram Equivalents) at 1,3, 6, 12,18, 24 months.
- Serious adverse events and mortality as related to implantation of the device and events associated with recovery and rehabilitation
- Device related complications
- Satisfactory deployment (Defined as radiographic imaging of the implant within the SI joint. Procedure time
- Fluoroscopy time (in minutes)
- Blood loss
- Type of anesthesia (local; MAC; general)
- Patient demographics
 - Age
 - Gender
 - Race
 - BMI
 - Smoking (y/n)
 - Year of Pain
 - Underlying diagnosis: degenerative sacroiliitis/sacroiliac joint disruption
 - Prior lumbar fusion (y/n)
 - Prior treatments (PT, FA, SIJ injection)

1. Timeline: Patients included in the study return for follow-up visits at 7-14 days, 1, 3 months, 6, 12, 18, and 24months post-treatment. Primary endpoint will be 6 month time point.
2. No randomization as treatment with the LinQ system will be performed regardless of whether the patient agrees to be in the research.

F. Risk/benefit assessment:

As appropriate, address the following parameters as each relates to the individual subject in the study.

1. Psychological risk: minimal, less than 1%
2. Social risk minimal, less than 1%
3. Potential benefit of participating in the study
 - a. To the individual subject and/or parent if any:

Improvement in the following domains:

 - a. Pain
 - b. Physical functioning
 - c. Emotional functioning
 - d. Patient global rating of improvement and satisfaction
 - e. Symptoms and adverse events
 - f. Patient disposition
 - b. To the population from which the subject is drawn: The study will provide

evidence to support a new treatment modality that is safe and effective. This

treatment modality also does not require repetition or multiple treatments unlike other treatments for sacroiliac joint dysfunction. It will also offer a salvage therapeutic option for patients who have failed other treatment modalities.

- c. To science, society, and humanity in general: Advancement of minimally invasive musculoskeletal techniques that may significantly reduce associated morbidity, mortality, and overall cost of treatment for chronic musculoskeletal related pain.

G. Location where study will be performed: Multisite

H. Collaboration: Multisite

I. Single IRB Review for a Multi-site study:

IRB local approval

J. Personnel who will conduct the study, including:

- 1. Indicate, by title, who will be present during study procedure(s): Study coordinator, attending physician, company representative, fellow physician (when available).
- 2. Primary responsibility for the following activities, for example:
 - a. Determining eligibility: PI, study attendings, senior trainees
 - b. Obtaining informed consent: Attendings at the study site including co-investigators, senior trainees at study site, and/or research coordinators
 - c. Providing on-going information to the study sponsor and the IRB: No Study Sponsors
 - d. Maintaining participant's research records: Research coordinator
 - e. Completing physical examination: Attendings and trainees at study site
 - f. Taking vital signs, height, weight: Clinic staff
 - g. Drawing / collecting laboratory specimens: Not applicable
 - h. Performing / conducting tests, procedures, interventions, questionnaires: Attending physician and fellow physicians at study site
 - i. Completing study data forms: Research coordinator
 - j. Managing study database: Research coordinator

K. Adverse Event Monitoring

Adverse events and unanticipated problems will be ascertained and handled per standard of care as applies to any procedure. Problems that would be considered serious and reported to the IRB include infection, new skeletal fracture resulting from procedure, unanticipated post-operative admission, and neurologic injury and would be monitored for on an ongoing basis as per standard of care. The reporting timeframe would be within two weeks of incident to allow for appropriate additional diagnostic testing and treatment while maintaining study responsiveness to adverse events.

If patient experiences an adverse event or post-procedural problem, this will be treated per standard of care. This would include standard of care treatment of any related injury and potential device explanation. Patient may opt out of study at any time voluntarily. This would be monitored and discussed on an ongoing basis in the setting of an adverse event or post-procedural problem.

III. Subject Participation

A. Recruitment:

1. Potential study participants will come from the existing patient population of the investigators in each individual practice.

Recruitment can be performed by interventional pain providers and will be offered to anyone who is a candidate for the LinQ fusion procedure and meet the inclusion and exclusion criteria for the study. This research studies the LinQ system, a legally-marketed device, determined by that health care practitioner to be in the best interests of the patient. Patients will undergo treatment with the LinQ fusion procedure regardless of participation in the research. Therefore, the procedures being conducted because of the research are limited to data collection and the use of the LinQ system is not a research procedure.

B. Informed consent process and timing of obtaining of consent

The following study personnel may participate in the consent process: PI, co-Investigators, senior trainees, research assistants, and research coordinator.

After it has been determined that the patient is a candidate for LinQ fusion procedure and they meet the inclusion and exclusion criteria, the patient will be offered the opportunity to participate in this study. An IRB approved consent form will be used for this study and obtained on all study patients prior to collecting any study related information or documentation. All questions that the potential study patient has will be addressed. Participation in the study is voluntary, study patients may withdraw at any time.

The clinician will determine if the patient has the capacity to proceed with informed consent. Only patients with capacity to proceed with informed consent will be included in study. Minors are not allowed to participate in the study. A legally appointed guardian, closest family member, or individual with power of attorney may not serve as a substitute.

Alternatives to Participation:

Alternatives to participation in research study is to not take part in this research.

C. Costs to Subjects:

The patient will not incur any costs because of research. The LinQ procedure will be performed regardless of participation in the research and standard charges will apply for the LinQ procedure. Eligibility criteria include insurance coverage for study procedure.

D. How new information will be conveyed to the study subject and how it will be documented:

New information regarding treatment options or significant results that may affect care will be conveyed and applied by standard of care guidelines. Standard of care includes appropriate, HIPAA compliant communication mediums. This information will be documented in the medical record as it applies to the patient's treatment per standard of care.

Payment, including a prorated plan for payment:

The subject will be paid \$250.00 at the 24 month visit for taking part in this research.

E. Payment for a research-related injury:

Study procedure is standard of care. Research-related injury will be handled as standard of care via accepted legal mechanisms, which include mediation, arbitration, or litigation for settlement.

IV. Data Collection and Protection

A. Data Management and Security:

Data will be collected from electronic medical record, during surgery, and self-report questionnaires. Confidentiality will be maintained by storing patient data on a cloud based secured, HIPPA compliant system. Identifiable data will not be sent outside any practice institution.

B. Procedures to protect subject confidentiality:

Patient identifiers may be included in master spreadsheet for reference to clinical chart if need arises for further review. Data will be de-identified with master spreadsheet containing patient identifiers linked to generated ID. A secondary spreadsheet will be generated containing pertinent study measures linked to the generated ID. The study coordinator will serve as the honest broker or buffer between master and secondary spreadsheets.

V. Data Analysis and Reporting

A. Statistical and Data Analysis:

Statistical analysis will include paired t-test of quantitative measures such as VAS pain score, Oswestry Disability Index, PROMIS 29, and quantitative secondary outcomes. ANOVA regression analysis will be performed to identify potential correlates of improved outcomes measures and adverse outcomes. IBM SPSS Statistics will be utilized to perform the analysis. Interim analysis will be performed on an anticipated monthly basis by a statistician. At no time will identifying information be transferred.

B. Outcome Measures:

i. Primary Outcome Measures

1. Binary success failure composite end point. A subject was considered a success if all of the following criteria were met
 - a. Reduction from baseline VAS SIJ pain by at least 20 mm
 - b. Absence of device related serious adverse events,
 - c. Absence of neurologic worsening related to the lumbosacral nerve roots,
 - d. Absence of surgical reintervention (removal, revision reoperation or supplemental fixation) for SIJ pain

ii. Secondary Outcome Measures

1. Improvement in baseline in VAS from baseline at 6 months
2. Oswestry Disability Index at 6 months follow up
3. PROMIS-29 at 6 months follow up
4. Patient Satisfaction with PGIC
5. Morphine milligram equivalent usage at all time points

C. Study results to participants:

Once final analysis completed, debriefing report will be given at follow up appointment or via telephone call. If no further contact maintained, copy of published manuscript will be sent to patients. Purpose of this will be to debrief patients as to study results.

D. Visit Schedule

	At least 7 days prior to Baseline	(within 4 weeks of surgery)									
Informed Consent	X										
Inclusion / Exclusion Review	X	X									
Urine Pregnancy test (if required)	X										
Surgery Information			X								
VAS	X	X		X	X	X	X	X	X	X	
PROMIS-29		X		X	X	X	X	X	X	X	
ODI	X	x		X	X	X	X	X	X	X	
Patient Satisfaction					X	X	X	X	X	X	

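### The only power calculation (Protocol II.C) is for a paired t-test on quantitative scores, so neither its 80% power nor its claim that fifty patients suffice covers the binary primary composite

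*Protocol*

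**What the plan says.** Section II.C contains the protocol's only sample size reasoning: "Power calculation based on paired T test, Alpha 0.05, Beta 0.2, Power 0.8, Effect Size 0.5, two sided yielded sample size of 34 patients". It does not name the outcome to which the effect size of 0.5 belongs. It then allows for 20% loss and states that "fifty patients would be sufficient to achieve study aims". The same section describes enrolment in open-ended terms: "Anticipated study enrollment will be ongoing patients for registry".

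Two places say what paired t-tests are for. II.C: "Statistical methods would include paired T tests for quantitative measures which include VAS score, Oswestry Disability Index, and Promis-29". V.A: "Statistical analysis will include paired t-test of quantitative measures such as VAS pain score", followed by ODI, PROMIS-29 and the quantitative secondary outcomes.

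The primary outcome is of another kind. V.B.i defines it as a "Binary success failure composite end point". A patient succeeds only by meeting all four criteria. The first is "Reduction from baseline VAS SIJ pain by at least 20 mm"; the other three are freedom from device-related serious adverse events, from lumbosacral neurologic worsening and from surgical reintervention. The timeline in II.E sets the time: "Primary endpoint will be 6 month time point". V.B.ii lists VAS improvement, ODI and PROMIS-29, each at 6 months, as secondary.

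**The concern.** A paired t-test compares two quantitative measurements on the same patient. The composite gives one success or failure per patient at 6 months. The change from baseline is already inside it, as a yes/no at 20 mm, and the other three parts are events after the procedure. It has no baseline value to pair, so the test used for sizing cannot be its test.

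The sufficiency sentence carries no qualification, and section I gives the purpose as evaluating both safety and efficacy. Three of the four composite criteria concern safety or reintervention, which a test on mean scores does not address. An ethics committee, or a reader of the eventual publication, could take 80% power and the adequacy of fifty patients as applying to the primary endpoint.

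**Working it through.** **1. Reproduce the stated figure.** Inputs from II.C: two-sided alpha 0.05, power 0.80, standardised effect d = 0.5. Power of a paired t-test comes from the noncentral t distribution with n − 1 degrees of freedom and noncentrality d√n.

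- n = 33: noncentrality 0.5 × √33 = 2.87, power 79.5%
- n = 34: noncentrality 0.5 × √34 = 2.92, power 80.8%

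The smallest n reaching 80% is 34, so the stated figure is right for this test.

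**2. Loss to follow-up.** 34 / (1 − 0.20) = 42.5, so 43 would be enough; fifty exceeds that. Fifty less 20% leaves 50 × 0.80 = 40 evaluable, with paired t-test power of 86.9%. The arithmetic in II.C is not at fault.

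**3. Match the calculation to the endpoints.**

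| Outcome | Status | Data per patient | Paired t-test applies? |
|---|---|---|---|
| VAS, ODI, PROMIS-29 at 6 months | Secondary (V.B.ii) | Quantitative, with baseline | Yes |
| Composite at 6 months | Primary (V.B.i) | One yes/no, no baseline | No |

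**4. Does a standardised change of 0.5 imply anything about the composite?** Assume normally distributed VAS change with mean 0.5 SD. The proportion reaching 20 mm is 1 − Φ((20 − 0.5 SD)/SD). The protocol gives no SD, so take a range:

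- SD 20 mm: 1 − Φ(0.5) = 31%
- SD 40 mm: 1 − Φ(0) = 50%

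The same sized effect is compatible with quite different rates on the VAS criterion alone, before the other three criteria are applied.

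**5. Could power for the composite be computed instead?** Only with a reference rate p0 and an expected rate p1, and the protocol gives neither. With assumed rates, 40 evaluable patients and an exact one-sample binomial test at one-sided 0.025:

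- p0 = 0.50 (reject at 27 or more successes): power 21% at p1 = 0.60, 70% at 0.70, 98% at 0.80
- p0 = 0.70 (reject at 34 or more): power 29% at p1 = 0.80

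The answer depends entirely on the assumptions, so adequacy can be neither shown nor refuted from the document.

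**6. What the planned size does deliver.** Exact (Clopper-Pearson) 95% limits for x successes in n are the 2.5% point of Beta(x, n − x + 1) and the 97.5% point of Beta(x + 1, n − x). The success rates are illustrative.

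| Success rate | 40 evaluable | 50 evaluable |
|---|---|---|
| 50% | 33.8% to 66.2% | 35.5% to 64.5% |
| 70% | 53.5% to 83.4% | 55.4% to 82.1% |
| 80% | 64.4% to 90.9% | 66.3% to 90.0% |

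With 40 evaluable, the intervals are about 27 to 32 points wide. The lower limit lies 16.5 points below the estimate at 70% (70.0 − 53.5), 15.6 below at 80% (80.0 − 64.4), and at most 16.7 below over all possible counts (at 25/40).

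**The case against.** II.C never says that the 80% belongs to the primary endpoint. The sentence about quantitative measures that follows it, together with V.A, already points to the scores, so the only real overreach is the phrase about sufficiency. The study is also a single-arm, post-market study of a marketed device. II.A states a largely descriptive objective, no success criterion is set for the composite, and open-ended enrolment means fifty may not bind. A statistical analysis plan, not among the documents reviewed, might give a basis for the primary analysis. Finally, interval limits describe what any study of this size delivers; they do not measure an error.

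Much of this stands, and it limits the point. No stated hypothesis is missed, no shortage of patients is shown, and nothing here faults the absence of a primary test that an analysis plan may contain. The core is not removed. The primary endpoint is plainly among the study's aims, and the sufficiency claim is unqualified. Its only support is a calculation for a type of outcome that the protocol itself lists as secondary. An analysis plan could add a basis for the composite, but II.C would still read as it does. That the study need not claim power for its primary endpoint is a reason to limit the claim.

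**Conclusion.** The concern holds. Within the protocol, the 80% power and the sufficiency of fifty patients are unsupported for the 6-month composite. The calculation is numerically correct but fits only quantitative change scores. The conclusion rests on the endpoint definitions in V.B and the use of paired t-tests in II.C and V.A, and on no assumed rate.

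The figures for the composite do rest on assumptions: 40 evaluable patients (the protocol's own 20% loss applied to fifty) and illustrative success rates of 50% to 80%. They show the precision on offer and do not show that it is inadequate. This should be fixed, but it is a matter of what the protocol claims and does not call for a change of design.

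**What to change.** Revise II.C in three respects.

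1. Name the outcome to which the effect size of 0.5 refers, and state that the 34/50 calculation and its 80% power apply to secondary mean changes only.
2. Remove the sufficiency sentence or limit it in the same way.
3. State what the planned size delivers for the primary composite. One possible wording: *With 40 evaluable of 50 enrolled, the exact (Clopper-Pearson) 95% CI for the 6-month success proportion would be 33.8% to 66.2% at 50% success, 53.5% to 83.4% at 70% and 64.4% to 90.9% at 80%.* If continuing enrolment leads to a different analysed number, give the limits for that number. Another interval method would also serve, provided actual limits are quoted.

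The cost is protocol wording. No added patients and no performance goal are required. The sponsor can no longer quote 80% power for the study as a whole, and the primary endpoint is then described by intervals roughly 27 to 32 points wide.

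### The VAS and ODI entry cuts appear to fall on the same baseline score that change is measured from, so the single-arm mean changes include some regression to the mean

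*Protocol*

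**What the plan says.** - **Entry cuts (Protocol II.D, Inclusion criteria).** Both are worded on the baseline score: "Baseline Low back/buttock pain score of at least 50 on 0-100 mm visual analog scale", and "Baseline Oswestry Disability Index (ODI) score of at least 30" per cent.
- **Reference for change (V.B).** The pain component of the primary composite is "Reduction from baseline VAS SIJ pain by at least 20 mm". The first secondary outcome is "Improvement in baseline in VAS from baseline at 6 months". The ODI outcome is listed at 6 months without naming a reference, but a paired test implies one.
- **Analysis (V.A).** "Statistical analysis will include paired t-test of quantitative measures such as VAS pain score, Oswestry Disability Index" and other measures. The design is single arm (II.B), so there is no control group against which to subtract a common drift.
- **Timing (V.D, Visit Schedule).** VAS and ODI are marked at two pre-surgery columns, one headed "At least 7 days prior to Baseline" and the other "within 4 weeks of surgery". The eligibility review is marked at both. The schedule does not say whether the VAS and ODI cuts are applied again at the second.
- **Consent (III.B).** Participation is offered "After it has been determined that the patient is a candidate for LinQ fusion procedure and they meet the inclusion and exclusion criteria". The schedule puts consent at the earlier of the two visits.

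The protocol does not formally define baseline.

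**The concern.** When patients are admitted because a noisy score exceeds a threshold, that score is biased upward as a measure of their usual level. A later score on the same scale is then lower on average with no treatment effect. In a controlled trial both arms share this fall and it cancels. Here it does not, and a paired t-test against zero counts it as improvement.

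What is at stake is mainly the mean VAS and ODI changes at 6 months, which are secondary outcomes but are likely to be read as device benefit. PROMIS-29 has no entry cut and is affected only indirectly. No inflation of a primary error rate is claimed.

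**Working it through.** **Inputs from the protocol.** VAS cut 50 mm; ODI cut 30%; responder threshold 20 mm; two-sided alpha 0.05, so 2.5% in the direction of improvement; 50 patients with 20% loss (II.C), so 50 × 0.8 = 40 evaluable.

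**The plan's own figure.** For a paired t-test with effect size 0.5, two-sided 0.05 and 80% power, the noncentral t gives power 79.5% at n = 33 and 80.8% at n = 34. The stated 34 reproduces and is not in question.

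**Assumed inputs.** The protocol gives no pre-selection mean, SD or between-visit correlation r. VAS: mean 55–75, SD 15–20, r 0.5–0.8. ODI: mean 40–55, SD 12–18, r 0.5–0.8. No true change.

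**Same reading for cut and reference.** With a = (cut − mean)/SD,

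spurious fall = (1 − r) × SD × φ(a)/(1 − Φ(a)).

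For VAS 60/20/0.6 (mean/SD/r): a = −0.5; φ(a)/(1 − Φ(a)) = 0.3521/0.6915 = 0.509; fall = 0.4 × 20 × 0.509 = 4.07 mm.

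Rejection rates come from simulation: normal scores clipped to 0–100, 10,000 trials of n = 40, improvement declared beyond t(0.975, 39).

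| Measure | Mean/SD/r | Spurious fall | Null trials declaring improvement |
|---|---|---|---|
| VAS | 55/20/0.5 (highest) | 6.5 mm | 60% |
| VAS | 60/20/0.6 | 4.1 mm | 33% |
| VAS | 60/20/0.7 | 3.1 mm | 26% |
| VAS | 75/15/0.7 | 0.5 mm | about 4% |
| VAS | 75/15/0.8 (lowest) | 0.3 mm | 4% |
| ODI | 45/15/0.6 | 1.7 points | 13% |

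The ODI range over its grid is 0.1 to 4.3 points.

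**Share reaching 20 mm.** At 60/20/0.6 with no true effect, 16.8% reach it with a shared reading and 12.6% with separate readings. Over the grid the shared reading adds 0.1 to 7.1 percentage points.

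**Cut enforced at both pre-surgery visits.** Over the grid the fall is 0.2 to 4.9 mm and 3% to 40% of null trials declare improvement. Neither reading is then free of selection.

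**Separate readings.** Let r_sb be the correlation between the two pre-surgery readings and r_g that of the gated reading with month 6. Then

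residual = (r_sb − r_g) × SD × φ(a)/(1 − Φ(a)).

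At 60/20 with r_g = 0.6, SD × φ(a)/(1 − Φ(a)) = 20 × 0.509 = 10.2:

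| r_sb | Separate readings: residual | Rejection | Cut at both: residual |
|---|---|---|---|
| 0.6 | 0.0 mm | about 2% | 3.0 mm |
| 0.7 | 1.0 mm | 5% | 3.5 mm |
| 0.8 | 2.0 mm | 11% | 3.9 mm |
| 0.9 | 3.1 mm | 20% | 4.3 mm |

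The share of the 4.1 mm that remains with separate readings is 0, 25, 50 and 75%. If both readings correlate equally with month 6, it makes no difference which one is gated. If the earlier correlates at 0.55 and the later at 0.60, then at r_sb 0.7, 0.8 and 0.9 gating the earlier leaves 1.5, 2.5 and 3.6 mm, and gating the later leaves 1.0, 2.0 and 3.1 mm.

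**The case against.** **The premise is an inference.** Section III.B has the criteria met before participation is offered, and consent is placed at the earlier visit. Read together, qualification may already precede a separate baseline reading, which is the design recommended here. This has force and lowers certainty. It does not settle the matter, because II.D words both cuts on the baseline score and the eligibility review is marked again at the second visit. The schedule's header row is incomplete in the copy available, and nothing is inferred from that.

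**The VAS items may differ.** The cut refers to low back/buttock pain and the primary criterion to SIJ pain. If these are separate items, the VAS bias is diluted. The ODI bias is not affected.

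**The reference could be left to the analysis plan.** This is partly right: if the cut applies to the baseline reading only, an analysis plan could name the earlier reading as reference. It could not undo a cut enforced at both visits, because the entry rule is fixed in the protocol.

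**The size is assumed and may be near zero.** This stands. The 55/20 setting implies that about 40% of candidates would score under 50 mm, and 60/20 about 31%. Patients already selected for fusion may score higher, which points to the low end of the range.

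**The gain is partial, and single-arm change has other problems.** This also stands. Readings taken close together usually correlate more than readings six months apart, so some bias survives. Placebo response and natural course are included whichever reading is used.

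**Conclusion.** The concern holds. On the natural reading of II.D with V.A and V.B, the reference score is a gated score, and the mean VAS and ODI changes include some regression to the mean. The size cannot be determined from the protocol. Under the assumed inputs it is most likely a few millimetres or less on VAS and a few points or less on ODI. That is small against the 20 mm threshold and could not explain a large improvement, but it is enough to distort a test of the mean change against zero. The sample size is not wrong, and the effect on the primary composite is slight. Confidence is moderate because the text gives mixed signals about which reading qualifies a patient. The change is worth making because it is cheap; it is not essential to the study's validity.

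**What to change.** Use the two pre-surgery readings already scheduled: one to qualify the patient, the other as reference.

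- **Preferred.** State in II.D that the VAS and ODI cuts apply to the earlier reading and are not applied again at the later visit. State in V.B that the 20 mm criterion and all paired comparisons use the later pre-surgery reading. This also agrees with III.B.
- **Alternative.** Keep the cuts on the baseline reading only, name the earlier, ungated reading as the reference, and align III.B. This gives the same reduction if both readings correlate equally with month 6, and a better one if the later reading correlates more strongly.
- **Either way.** Do not enforce the cut at both visits. State that mean change still includes residual regression to the mean, placebo response and natural course.

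**Cost.** No new visits or data. The preferred option rewords two inclusion criteria and adds a sentence or two in V.B. Some patients would then have a reference VAS under 50 mm: at 60/20, 19%, 16%, 13% or 9% for pre-surgery correlations of 0.6, 0.7, 0.8 or 0.9; at 75/15/0.7, 3%. For ODI at 45/15, 10% (correlation 0.6) or 7% (0.8) would fall under 30%. A 20 mm fall is harder to reach from a lower start; that loss under a real treatment effect has not been quantified. The alternative leaves the cuts unchanged but takes the reference further from surgery. Under either option the reported improvement will be slightly smaller.
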